8.2. Statistical Analyses

A 1-way analysis of variance (ANOVA) will be used to compare the natural log transformed PF-06865571 AUC_{inf} , AUC_{last} , and C_{max} , as data permit, for each of the hepatic impairment cohorts (Test) to the cohort without hepatic impairment (Reference). Estimates of the adjusted mean differences (Test - Reference), and corresponding 90% confidence intervals, will be obtained from the model. These will be exponentiated to provide estimates of the ratio of adjusted geometric means (Test/Reference) and 90% confidence intervals for the ratios.

Residuals from the models will be examined for normality and the presence of outliers via visual inspection of plots of residuals vs predicted values and normal probability plots of residuals but these will not be included in the clinical study report. If there are major deviations from normality or outliers then the effect of these on the conclusions will be investigated through alternative transformations and/or analyses excluding outliers. Justification for any alternative to the planned analysis will be given in the report of the study.

The following PK parameters will be summarized by hepatic function group:

Table 3. PK Parameters to be Summarized Descriptively by Group

Parameter	Summary Statistics
AUC _{last} , AUC _{inf} ,	N, arithmetic mean, median, cv%, standard deviation, minimum, maximum, geometric mean and geometric cv%.
CCI	

Box and whisker plots for individual participant parameters (AUC_{inf}, AUC_{last} and C_{max}) may be presented by hepatic function group and overlaid with geometric means.

Supporting data from the estimation of AUC_{inf} will be listed by group: terminal phase rate constant (k_{el}); goodness of fit statistic from the log-linear regression (r^2); the percent of AUC_{inf} based on extrapolation ($AUC_{extrap\%}$); and the first, last, and number of time points used in the estimation of k_{el} . This data may be included in the clinical study report.

Presentations for PF-06865571 concentrations will include:

- a listing of all concentrations sorted by hepatic function group (from without hepatic impairment 1st, followed by mild/C2, moderate/C3 and finally severe/C4, present in heading), participant ID and nominal time postdose. The concentration listing will also include the actual times. Deviations from the nominal time will be given in a separate listing.
- a summary of concentrations by hepatic function group and nominal time postdose, where the set of statistics will include n, mean, median, standard deviation, coefficient of variation (cv), minimum, maximum and the number of concentrations above the lower limit of quantification.

- median concentrations time plots (on both linear and semi-log scales) against nominal time postdose by hepatic function group (all hepatic function groups on the same plot per scale, based on the summary of concentrations by hepatic function group and time postdose).
- mean concentrations time plots (on both linear and semi-log scales) against nominal time postdose by hepatic function group (all hepatic function groups on the same plot per scale, based on the summary of concentrations by hepatic function group and time postdose).
- individual concentration time plots by hepatic function group (on both linear and semilog scales) against actual time postdose (there will be separate spaghetti plots for each hepatic function group per scale).

For summary statistics, median and mean plots by sampling time, the nominal PK sampling time will be used, for individual participant plots by time, the actual PK sampling time will be used.

8.3. Safety Analysis

A set of summary tables split by hepatic function group will be produced to evaluate any potential risk associated with the safety and toleration of administering PF-06865571.

8.3.1. Treatment and Disposition of Participants

Participant evaluation groups will show end of study participant disposition. Frequency counts will be presented for participants discontinuation(s) by hepatic function group.

Data will be reported in accordance with the sponsor reporting standards.

8.3.2. Demographic and Clinical Examination Data

A summary of demographic data will be provided for age, race, weight, body mass index, and height. Each will be summarized by hepatic function group and 'Total Participants' in accordance with the sponsor reporting standards.

8.3.3. Discontinuation(s)

Participant discontinuations due to adverse events will be detailed and summarized by hepatic function group.

Data will be reported in accordance with the sponsor reporting standards.

8.3.4. Adverse Events

Adverse events will be reported in accordance with the sponsor reporting standards by hepatic function group.

8.3.5. Laboratory Data

Laboratory data will be listed and summarized by hepatic function group in accordance with the sponsor reporting standards. Baseline will be the planned predose measurement obtained on Day 1.

8.3.6. Vital Signs Data

Baseline value will be the planned predose measurement obtained on Day 1.

Maximum absolute values and changes from baseline for seated vital signs will be summarized descriptively by hepatic function group using categories as defined in **0**. Numbers and percentages of participants meeting the categorical criteria will be provided. All planned and unplanned postdose time-points will be counted in these categorical summaries. All values meeting the criteria of potential clinical concern will be listed.

These data will be listed in accordance with the sponsor reporting standards.

8.3.7. ECG Data

Baseline value will be the planned predose measurement obtained on Day 1.

Changes from baseline for the ECG parameters QT interval, heart rate, derived QTcF interval, PR interval, and QRS complex will be summarized by treatment and time.

The number (%) of participants with maximum postdose QTcF values and maximum increases from baseline in the following categories will be tabulated by treatment:

Safety QTcF Assessment

Degree of Prolongation	Mild (msec)	Moderate (msec)	Severe (msec)
Absolute value	>450-480	>480-500	>500
Increase from baseline		30-60	>60

In addition, the number of participants with uncorrected and corrected QT values > 500 msec will be summarized and listed.

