- Full physical (PE) exam at Screen; at all other time points, limited PE for findings during previous PE or new/open AEs *only*, at Investigator discretion.
- On Day 3**, procedures limited to Cohort 1, *only*; **on Day 4**, procedures limited to Cohorts 2-4, *only*.
- In Cohorts 2-4 *only*, procedures to be completed *only if* participant is discharged on Day 3 and returns for outpatient visit on Day 4.
- Confirmation of appropriate contraception use *only*.
- Meals/snacks to be served at clock times matching approximately 0H, 4H, 7H, 10H, and 14H (optional) relative to dosing on Day 1 (while inpatient).
- Dosing to occur with standard morning meal provided approximately 30 minutes prior to 0H, and completed approximately 10 minutes prior to dosing.

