- 6. Other acute or chronic medical or psychiatric condition including recent (within the past year) or active suicidal ideation or behavior or laboratory abnormality that may increase the risk associated with study participation or investigational product administration or may interfere with the interpretation of study results and, in the judgment of the investigator, would make the participant inappropriate for entry into this study.

5.2.2. Additional Exclusion Criteria for Participants with Impaired Hepatic Function (Cohorts 2, 3, and 4 Only)

Participants presenting with any of the following will ***not*** be included in the study:

- 1. Hepatic carcinoma ***or*** hepatorenal syndrome ***or*** limited predicted life expectancy (defined as less than 1 year in Cohorts 2 & 3 and less than 6 months for Cohort 4 only).
- 2. A diagnosis of hepatic dysfunction secondary to any acute ongoing hepatocellular process that is documented by medical history, physical examination, liver biopsy, hepatic ultrasound, computerized tomography scan, or magnetic resonance imaging (MRI).

3. History of surgery that would be expected to alter absorption, distribution, metabolism, or excretion (ADME) properties of PF-06865571 (eg, status post porta-caval shunt surgery);

NOTE: Participants with a transjugular intrahepatic portosystemic shunt (TIPS) are permitted provided that they meet the Child-Pugh criteria.
4. History of gastrointestinal hemorrhage due to esophageal varices or peptic ulcers less than **4 weeks** prior to Screening.
5. Signs of clinically active Grade 3 or Grade 4 hepatic encephalopathy (ie, > Grade 2 Portal Systemic Encephalopathy score; refer to [Appendix 8](#)).
6. Severe ascites and/or pleural effusion, except for those categorized in Cohort 4 who may be enrolled provided participant is medically stable, per the investigators' medical judgment.
7. Participants who have previously had a transplanted kidney, liver, or heart.
8. Screening *supine* 12-lead ECG demonstrating a QTcF interval >480 msec or a QRS interval >120 msec. If QTcF exceeds 480 msec, or QRS exceeds 120 msec, the ECG should be repeated 2 more times and the average of the 3 QTcF or QRS values should be used to determine eligibility.

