8.2.3. Electrocardiograms

Supine 12-lead ECGs should be collected at times specified in the [SoA](#) section of this protocol using an ECG machine that automatically calculates the heart rate and measures PR, QT, and QTcF intervals and QRS complex. All scheduled ECGs should be performed after the participant has rested quietly for at least 10 minutes in a supine position.

To ensure safety of the participants, a qualified individual at the investigator site will make comparisons to baseline measurements. Additional ECG monitoring will occur if a) a postdose QTcF interval is increased by ≥ 30 msec from the baseline **and** is >450 msec; or b) an absolute QTcF value is ≥ 500 msec for any scheduled ECG. If either of these conditions occurs, then 2 additional ECGs will be collected approximately 2 to 4 minutes apart to confirm the original measurement. If the QTcF values from these repeated ECGs remain above the threshold value, then a single ECG must be repeated at least hourly until QTcF values from 2 successive ECGs fall below the threshold value that triggered the repeat measurement.

If a postdose QTcF interval remains ≥ 30 msec from the baseline **and** is >450 msec; or b) an absolute QTcF value is ≥ 500 msec for any scheduled ECG for greater than 4 hours (or sooner, at the discretion of the investigator), or QTcF intervals get progressively longer, the participant should undergo continuous ECG monitoring. A cardiologist should be consulted if QTcF intervals do not return to less than the criterion listed above after 8 hours of monitoring (or sooner, at the discretion of the investigator).

In some cases, it may be appropriate to repeat abnormal ECGs to rule out improper lead placement as contributing to the ECG abnormality. It is important that leads be placed in the same positions each time in order to achieve precise ECG recordings. If a machine-read QTcF value is prolonged, as defined above, repeat measurements may not be necessary if a qualified medical provider's interpretation determines that the QTcF values are in the acceptable range.

ECG values of potential clinical concern are listed in [Appendix 7](#).

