9.4.3.1. Electrocardiogram Analyses

Changes from baseline for the ECG parameters QT interval, heart rate, derived QTcF interval, PR interval, and QRS complex will be summarized by treatment and time.

The number (%) of participants with maximum postdose QTcF values and maximum increases from baseline in the following categories will be tabulated by treatment:

Safety QTcF Assessment

Degree of Prolongation	Mild (msec)	Moderate (msec)	Severe (msec)
Absolute value	>450-480	>480-500	>500
Increase from baseline		30-60	>60

In addition, the number of participants with uncorrected and corrected QT values >500 msec will be summarized.

CCI

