8. STATISTICAL METHODOLOGY AND STATISTICAL ANALYSES

8.1. Statistical Methods

For all outputs produced, the following ordering will be used:

Without Hepatic Impairment

Mild Hepatic Impairment

Moderate Hepatic Impairment

Severe Hepatic Impairment.

The effect of the hepatic impairment on PK parameters will be assessed by constructing 90% confidence intervals around the estimated difference between each of the Test (impaired groups) and the Reference (normal hepatic function group) using a one-way ANOVA model based on natural log transformed data.

The relationship between PK parameters and hepatic function parameters (eg, serum albumin concentration, or prothrombin time) will be determined by a linear regression model.

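### Do the ECG tables need a new rule for grouping and for repeat ECGs?

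*SAP*

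**What the plan says.** SAP 8.3.7 sets a categorical QTcF table in which the number (%) of "participants with maximum postdose QTcF values and maximum increases from baseline in the following categories will be tabulated by treatment". Changes from baseline in the ECG intervals and heart rate "will be summarized by treatment and time"; this wording is in Protocol 9.4.3.1 and again in SAP 8.3.7. The bands are >450-480, >480-500 and >500 msec for the absolute value, and 30-60 and >60 msec for the increase.

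Other parts of the plan bear on how to read this:

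- SAP 8.3 opens with "A set of summary tables split by hepatic function group will be produced".
- SAP 8.1 fixes the order from no impairment to severe impairment: "For all outputs produced, the following ordering will be used".
- SAP 8.3.6, for the vital-sign categories, adds "All planned and unplanned postdose time-points will be counted in these categorical summaries". SAP 8.3.7 has no such sentence.
- The Schedule of Activities has one post-dose ECG per completer. Under footnote c, Day 3 (48 h) is for Cohort 1, and on Day 4 (72 h) there are "procedures limited to Cohorts 2-4".
- Protocol 8.2.3 calls for repeats if post-dose QTcF has risen by at least 30 msec and exceeds 450 msec, or is at least 500 msec: "then 2 additional ECGs will be collected approximately 2 to 4 minutes apart to confirm the original measurement". Repeats may be unnecessary if a qualified provider finds the value acceptable.
- For screening, Protocol 5.2.2 says "the average of the 3 QTcF or QRS values should be used to determine eligibility"; 5.2.1 has a similar rule.

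**The concern.** Two things look wrong at first.

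**Grouping.** The secondary objective is safety in impaired participants relative to participants without impairment. A one-column table cannot serve it. SAP 8.3.7 is also out of step with SAP 8.3.1 to 8.3.6, which are organised by hepatic function group.

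**Which reading counts.** With one planned post-dose ECG, the maximum has content only if repeats or unplanned tracings count. The trigger for repeats overlaps the bands of the table, so the silence concerns the participants of most interest. The documents show three uses of extra readings: averaging at screening, confirmation after dosing, and counting all time points for vital signs. In an open-label study a rule left open could be chosen after the values are seen. In a cohort of 6, one participant moves a cell by 16.7 percentage points.

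**Working it through.** The plan gives no figure to reproduce here. The check sets the texts side by side and then sizes the ambiguity.

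**Grouping.** Treatment has one level (Protocol 4.3: a single 100 mg dose). A literal table would have one column of about 24, where one participant is 1/24 = 4.2%. SAP 8.3 governs all its subsections and calls for a split by hepatic function group, and SAP 8.1 orders all outputs by that group. An analyst who follows SAP 8.3 produces four columns, where one participant is 1/6 = 16.7%, 1/4 = 25% (Cohort 4 minimum) or 1/8 = 12.5% (Cohort 1 maximum).

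**Candidate readings of the maximum.**

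1. Highest of all post-dose readings: the ordinary meaning of the word, and the rule of SAP 8.3.6.
2. Planned reading only: this would make the word redundant for completers.
3. Mean of three: found only in the screening criteria (Protocol 5.2.1 and 5.2.2). Protocol 8.2.3 uses post-dose repeats to confirm a value and decide on further monitoring, and does not average them.

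**Worked example.** Baseline 448, planned 481, repeats 470 and 468 msec. The trigger is met: 481 - 448 = +33, which is at least 30, and 481 > 450.

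- Maximum: 481 and +33, so Moderate on both rows.
- Planned only: 481 and +33, the same cells.
- Mean of three: (481 + 470 + 468)/3 = 473 and 473 - 448 = +25, so Mild on absolute value and no increase category.

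Only the averaging rule, which the post-dose text does not contain, moves this participant.

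**Simulation.** No QTcF variances are in the documents, so these are assumptions: true mean 430 or 445 msec, between-participant SD 18, visit-to-visit SD 8 or 12, reading-to-reading SD 5 or 10, baseline no higher than 480, no drug effect. That gives eight scenarios.

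| Quantity | Range |
|---|---|
| Trigger probability per participant | 0.0056 to 0.0716 |
| At least 1 trigger among 18 impaired, 1 - (1 - p)^18 | 10% to 74% |
| Category differs, maximum vs planned, among triggered | 2% to 12% |
| Category differs, maximum vs mean of three, among triggered | 34% to 71% |

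The chance of a trigger is not the chance of a changed category. Multiplying the two within a scenario gives, for at least 1 of 18 and maximum versus planned:

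- Lowest: 1 - (1 - 0.0056 × 0.02)^18 = 0.2%.
- Highest: 1 - (1 - 0.0716 × 0.115)^18 = 14%.

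Against the mean of three the same product runs from 5% to 54%. The simulation ignores the provider-review exception, so it overstates how often repeats occur.

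**The case for a change.** The best argument for a change is that one sentence before database lock would settle the matter at almost no cost. SAP 8.3.6 also speaks of maximum values, yet its authors still added the sentence on unplanned time points. SAP 8.3.7 requires a listing only above 500 msec, so a reclassification between 450 and 500 msec would not show in a required listing. Cohorts 2-4 may enter with QTcF up to 480 msec, against 450 in Cohort 1, so some start close to a cut-off. Protocol 9.4.3 defers to sponsor data standards, but their content is not in the documents and cannot be relied on to fill the gap.

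These facts stand, and aligning the two sections would be tidy. They do not show that the text as written leads to a wrong table. Copying the SAP 8.3.6 sentence would not settle everything either: tracings 2 to 4 minutes apart could be taken as replicates at one time point, and Protocol 8.2.3 allows repeats to rule out faulty lead placement. An analyst still has to count each valid reading and leave out a technically faulty one, which is ordinary practice.

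The planned post-dose ECG falls at 48 h in one cohort and 72 h in the others. That is a separate matter of timing, visible in the Schedule of Activities.

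**Conclusion.** No change follows. The grouping phrase is a clerical slip that SAP 8.1 and 8.3 already override, and correcting it alters no result. The silence on repeats is a gap that the word maximum fills sensibly: take the highest valid post-dose reading.

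The realistic ambiguity, maximum versus planned reading, changes a category in about 2% to 12% of triggered participants. That is a 0.2% to 14% chance of touching any of 18 impaired participants, under assumed variances and no drug effect. Without repeat or unplanned ECGs the effect is zero. The larger 34% to 71% depends on an averaging rule that the plan uses only for eligibility.

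The table is a descriptive secondary safety summary. SAP 4.1 and 4.2 plan no hypothesis test and no decision rule, QT or QTc values above 500 msec are summarised and listed separately, and the primary PK comparison is untouched.

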8.3.8. Other Safety Data

None.

8.3.9. Concomitant Treatments

All concomitant medication(s) as well as non-drug treatment(s) will be provided in the listings.

8.3.10. Screening and Other Special Purpose Data

Prior medication(s) and non-drug treatment(s), serum FSH concentrations, serum B-hCG for all females will be obtained at Screening. These data will only be listed.

Urine drug screen, urine B-hCG for women of child bearing potential and physical examination findings will be collected at baseline or prior to baseline visit. These data will not be brought in-house, and therefore will not be listed.

10. APPENDICES

Appendix 1: SAS CODE FOR ANALYSES

An example of the PROC GLM code is provided below:

```
proc glm data=tab.pk;
       class group;
       model 1&var=group/ss3 clparm alpha=0.1;
       Ismeans group;
       estimate 'Mild vs Normal'
                                          group -1 1 0 0;
       estimate 'Moderate vs Normal'
                                          group -1 0 1 0;
       estimate 'Severe vs Normal'
                                          group -1 0 0 1;
       ods output Estimates = est&var;
       ods output FitStatistics = fit&var;
       ods output ModelANOVA = tst&var;
       ods output OverallANOVA = overall&var;
run;
An example of the PROC REG code is provided below:
proc reg data=tab.pk;
       model l&var=&HepaticFunction/clb alpha=0.1;
       ods output ParameterEstimates = param&var;
       ods output FitStatistics = fit&var;
       ods output ANOVA = reg\&var;
run;
```

Appendix 2: Categorical Classes for Vital Signs of Potential Clinical Concern

Categories for Vital Signs

Systolic BP (mm Hg)	min. <90	
Systolic BP (mm Hg)	max. decrease ≥30	max. increase ≥30
change from baseline		
Diastolic BP (mm Hg)	min. <50	
Diastolic BP (mm Hg)	max. decrease ≥20	max. increase ≥20
change from baseline		
Seated pulse rate (bpm)	min. <40	max. >120

Measurements that fulfill these criteria are to be listed in report.
